8.3.2 Preparation

Refer to current nivolumab package insert. Nivolumab Injection: 40 mg/4 mL, 100 mg/10 mL, and 240 mg/24 mL solution in a single-dose vial.

Visually inspect drug product solution for particulate matter and discoloration prior to administration. Nivolumab is a clear to opalescent, colorless to pale-yellow solution. Discard the vial if the solution is cloudy, discolored, or contains extraneous particulate matter other than a few translucent-to-white, proteinaceous particles. Do not shake the vial.

During induction phase, nivolumab dosing is 3mg/kg IV every 3 weeks x 4 cycles (concurrent with ipilimumab and cabozantinib). During the maintenance phase, nivolumab dosing is 480mg IV every 4 weeks (concurrent with cabozantinib).

- Withdraw the required volume of nivolumab and transfer into an intravenous container.
- Dilute nivolumab with either 0.9% Sodium Chloride Injection, USP or 5% Dextrose Injection, USP to prepare an infusion with a final concentration ranging from 1 mg/mL to 10 mg/mL. The total volume of infusion must not exceed 160 mL.
- For adult and pediatric patients with body weights less than 40 kg, the total volume of infusion must not exceed 4 mL/kg of body weight.
- Mix diluted solution by gentle inversion. Do not shake.
- Discard partially used vials or empty vials of nivolumab.

Nivolumab injection is to be administered as an IV infusion through a 0.2-micron to 1.2-micron pore size, low-protein binding in-line filter at the protocol-specified doses and infusion times. It is not to be administered as an IV push or bolus injection.

8.3.3 Storage and Stability

The product does not contain a preservative.

After preparation, store the nivolumab infusion either:

- at room temperature for no more than 8 hours from the time of preparation. This includes room temperature storage of the infusion in the IV container and time for administration of the infusion or
- under refrigeration at 2°C to 8°C (36°F to 46°F) for no more than 24 hours from the time of infusion preparation.

Do not freeze.

8.3.4 Handling and Disposal

Preparation should be performed by trained personnel in accordance with good practices rules, especially with respect to asepsis.

8.3.5 Administration

Administer the infusion over 30 minutes through an intravenous line containing a sterile, non-pyrogenic, low protein binding in-line filter (pore size of 0.2 micrometer to 1.2 micrometer).

- Do not coadminister other drugs through the same intravenous line.
- Flush the intravenous line at end of infusion.
- When administered in combination with ipilimumab, infuse nivolumab first followed by ipilimumab on the same day. Use separate infusion bags and filters for each infusion.

8.3.6 Adverse Events and Management

Please see the package insert for a complete list of possible adverse events and guidance on adverse event management. Refer to Table 8-8 and ASCO/NCCN guidelines [18]. Also refer to section 8.5 for management guidance on potential overlapping adverse events from nivolumab, ipilimumab and cabozantinib.

Most common adverse reactions ($\geq 20\%$) in patients were:

- Nivolumab as a single agent: fatigue, rash, musculoskeletal pain, pruritus, diarrhea, nausea, asthenia, cough, dyspnea, constipation, decreased appetite, back pain, arthralgia, upper respiratory tract infection, pyrexia, headache, and abdominal pain.
- Nivolumab in combination with ipilimumab are fatigue, rash, diarrhea, nausea, pyrexia, musculoskeletal pain, pruritus, abdominal pain, vomiting, cough, arthralgia, decreased appetite, dyspnea.

No dose reductions are permitted. Interrupt or slow the rate of infusion in patients with mild or moderate infusion reactions. Discontinue in patients with severe or life-threatening infusion reactions.

Grade 2 and above immune related adverse events (irAEs) may/will require drug hold/discontinuation and administration of high dose corticosteroids (1-2mg/kg/day of prednisone or equivalent) tapered off over a 4-6 week period. Patient are to be completely off prednisone unless used for adrenal replacement purposes prior to resuming any immunotherapy, unless discussed with the Principal Investigator, [name]. Additional immune modulatory agents may be required for treatment of irAEs that are refractory to corticosteroids, such as infliximab for immune colitis and mycophenylate for immune hepatitis. Refer to guidance below in Table 8-8 and ASCO/NCCN guidelines. After recovery from irAE during the nivolumab/ipilimumab induction phase, patients will be permitted to receive maintenance nivolumab if the irAE was most likely due to ipilimumab (e.g. immune colitis or hepatitis) and patient is receiving clinical benefit with the therapy.

During the Induction Period (Nivo-Ipi-Cabo treatment), the subject should stay on schedule and follow procedures as outlined. Drug dosing may be omitted based on toxicity guidance per protocol. If Nivolumab is restarted in the induction phase, the dose will remain at 3mg/kg for the duration of the induction phase.

During the induction phase, if an Adverse Event requires all drug to be held, and the toxicity has recovered to Grade 1 or baseline prior to the next scheduled treatment visit and the patient is eligible for Nivolumab and/or Ipilimumab, please consult study chair for approval to restart prior to the next scheduled treatment visit. If a subject is eligible to restart Nivolumab and Ipilimumab after a delay, then all subsequent visits/procedures may be shifted, including the scans, in order to complete all 4 induction cycles. The scans may be done earlier, at the investigator's discretion.

During the Maintenance phase (Nivo+Cabo treatment), starting at cycle week 13, treatment/assessment cycle date may be shifted to account for recovery from immunotherapy related toxicity. The one exception is that scans should remain every 12 weeks according to calendar days.

Table 8-8 Adverse event management for nivolumab [Package Insert, 2018].

Adverse Reaction	Severity*	Dose Modification
Colitis	Grade 2 diarrhea or colitis	Withhold dose ^a
	Grade 3 diarrhea or colitis	Withhold dose ^a when administered as a single agent Permanently discontinue when administered with ipilimumab
	Grade 4 diarrhea or colitis	Permanently discontinue
Pneumonitis	Grade 2 pneumonitis	Withhold dose ^a
	Grade 3 or 4 pneumonitis	Permanently discontinue
Hepatitis/non-HCC ^b	Aspartate aminotransferase (AST) or alanine aminotransferase (ALT) more than 3 and up to 5 times the upper limit of normal (ULN) or total bilirubin more than 1.5 and up to 3 times the ULN	Withhold dose ^a
	AST or ALT more than 5 times the ULN or total bilirubin more than 3 times the ULN	Permanently discontinue
Hepatitis/ HCC ^b	
 If AST/ALT is within normal limits at baseline and increases to more than 3 and up to 5 times the ULN If AST/ALT is more than 1 and up to 3 times ULN at baseline and increases to more than 5 and up to 10 times the ULN If AST/ALT is more than 3 and up to 5 times ULN at baseline and increases to more than 8 and up to 10 times the ULN 	Withhold dose ^c
	If AST or ALT increases to more than 10 times the ULN or total bilirubin increases to more than 3 times the ULN	Permanently discontinue
Hypophysitis	Grade 2 or 3 hypophysitis	Withhold dose ^a
	Grade 4 hypophysitis	Permanently discontinue
Adrenal Insufficiency	Grade 2 adrenal insufficiency	Withhold dose ^a
	Grade 3 or 4 adrenal insufficiency	Permanently discontinue
Type 1 Diabetes Mellitus	Grade 3 hyperglycemia	Withhold dose ^a
	Grade 4 hyperglycemia	Permanently discontinue
Nephritis and Renal Dysfunction	Serum creatinine more than 1.5 and up to 6 times the ULN	Withhold dose ^a
	Serum creatinine more than 6 times the ULN	Permanently discontinue
Skin	Grade 3 rash or suspected Stevens-Johnson syndrome (SJS) or toxic epidermal necrolysis (TEN)	Withhold dose ^a
	Grade 4 rash or confirmed SJS or TEN	Permanently discontinue
Encephalitis	New-onset moderate or severe neurologic signs or symptoms	Withhold dose ^a
	Immune-mediated encephalitis	Permanently discontinue
Other	Other Grade 3 adverse reaction	
	First occurrence	Withhold dose ^a
	Recurrence of same Grade 3 adverse reactions	Permanently discontinue
	Life-threatening or Grade 4 adverse reaction	Permanently discontinue
	Grade 3 myocarditis	Permanently discontinue
	Requirement for 10 mg per day or greater prednisone or equivalent for more than 12 weeks	Permanently discontinue
	Persistent Grade 2 or 3 adverse reactions lasting 12 weeks or longer	Permanently discontinue

* Toxicity was graded per National Cancer Institute Common Terminology Criteria for Adverse Events. Version 4.0 (NCI CTCAE v4).

a Resume treatment when adverse reaction improves to Grade 0 or 1.

b HCC: hepatocellular carcinoma.

c Resume treatment when AST/ALT returns to baseline.

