8.4.6 Adverse Events

Please see the package insert for a complete list of possible adverse events and guidance on adverse event management. Refer to Table 8-9 and ASCO/NCCN guidelines [18]. Also refer to section 8.5 for management guidance on potential overlapping adverse events from nivolumab, ipilimumab and cabozantinib.

Most common adverse reactions ($\geq 5\%$) with ipilimumab as a single agent are fatigue, diarrhea, pruritus, rash, and colitis. Additional common adverse reactions at the 10 mg/kg dose ($\geq 5\%$) include nausea, vomiting, headache, weight loss, pyrexia, decreased appetite, and insomnia.

Most common adverse reactions ($\geq 20\%$) with ipilimumab in combination with nivolumab are fatigue, rash, diarrhea, nausea, pyrexia, musculoskeletal pain, pruritus, abdominal pain, vomiting, cough, arthralgia, decreased appetite, dyspnea.

No dose reductions are permitted. Interrupt or slow the rate of infusion in patients with mild or moderate infusion reactions. Discontinue in patients with severe or life-threatening infusion reactions.

Grade 2 and above immune related adverse events (irAEs) may/will require drug hold/discontinuation and administration of high dose corticosteroids (0.5-2mg/kg/day of prednisone or equivalent) tapered off over a 4-6 week period. Patient are to be completely off prednisone unless used for adrenal replacement purposes prior to resuming any immunotherapy, unless discussed with the Study Chair. Additional immune modulatory agents may be required

for treatment of irAEs that are refractory to corticosteroids, such as infliximab for immune colitis and mycophenylate for immune hepatitis. Refer to guidance below in Table 8-9 and ASCO/NCCN guidelines.

During the Induction Period (Nivo-Ipi-Cabo treatment), the subject should stay on schedule and follow procedures as outlined. Drug dosing may be omitted based on toxicity guidance per protocol. If Nivolumab is restarted in the induction phase, the dose will remain at 3mg/kg for the duration of the induction phase.

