During the induction phase, if an Adverse Event requires all drug to be held, and the toxicity has recovered to Grade 1 or baseline prior to the next scheduled treatment visit and the patient is eligible for Nivolumab and/or Ipilimumab, please consult study chair for approval to restart prior to the next scheduled treatment visit. If a subject is eligible to restart Nivolumab and Ipilimumab after a delay, then all subsequent visits/procedures may be shifted, including the scans, in order to complete all 4 induction cycles. The scans may be done earlier, at the investigator's discretion.

During the Maintenance phase (Nivo+Cabo treatment), starting at cycle week 13, treatment/assessment cycle date may be shifted to account for recovery from immunotherapy related toxicity. The one exception is that scans should remain every 12 weeks according to calendar days.

Table 8-9 Adverse event management for ipilimumab [Package Insert, 2018].

Target/Organ System	Adverse Reaction (CTCAE v4)	Treatment Modification
Endocrine	Symptomatic endocrinopathy	Withhold YERVOY Resume YERVOY in patients with complete or partial resolution of adverse reactions (Grade 0 to 1) and who are receiving less than 7.5 mg prednisone or equivalent per day.
	
 • Symptomatic reactions lasting 6 weeks or longer • Inability to reduce corticosteroid dose to 7.5 mg prednisone or equivalent per day 	Permanently discontinue YERVOY
Ophthalmologic	Grade 2 through 4 reactions 
 • not improving to Grade 1 within 2 weeks while receiving topical therapy or • requiring systemic treatment 	Permanently discontinue YERVOY
All Other	Grade 2	Withhold YERVOY Resume YERVOY in patients with complete or partial resolution of adverse reactions (Grade 0 to 1) and who are receiving less than 7.5 mg prednisone or equivalent per day.
	
 • Grade 2 reactions lasting 6 weeks or longer • Inability to reduce corticosteroid dose to 7.5 mg prednisone or equivalent per day • Grade 3 or 4 	Permanently discontinue YERVOY

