8.5 Overlapping adverse event management guidance

Many adverse events overlap between nivolumab/ipilimumab and cabozantinib. However, the mechanisms of action of the adverse events are likely different between these two classes of therapies and they require separate management plans. For example grade 3 diarrhea attributed to ipilimumab requires drug discontinuation, a course of high dose corticosteroids and supportive care, whereas grade 3 diarrhea attributed to cabozantinib requires temporary drug hold and supportive care alone. For adverse events that are most likely to occur with one class of therapy, the adverse event management should follow for that agent. An example is a grade 3-4 electrolyte abnormality, which is more common with cabozantinib. In this case, all three drugs should be temporarily held, but no corticosteroids given as this is likely not an immune related event. However, in patients with life threatening events (grade 4) or no improvement with drug hold after 5 days, then corticosteroids should be considered as it may be a rare irAE. In situations where a grade 3-4 adverse event could be due to either class of therapy, all drugs will need to be held and high dose corticosteroids administered if recommended by standard nivolumab or ipilimumab guidelines. After recovery of adverse event to grade 1 or baseline, cabozantinib can be reinitiated even if the corticosteroid taper has not been completed. The cabozantinib may need to be dose reduced if indicated by the included dosing guidelines. For some situations, such as grade 2 elevated transaminase levels, it may be appropriate to hold all study drugs, but monitor for improvement prior initiation of corticosteroids. In patients where nivolumab/ipilimumab or nivolumab cannot be restarted, cabozantinib would continue alone as outlined in the protocol treatment schema unless permanent discontinuation indicated (section 8.2). Similarly, in patients where cabozantinib cannot be restarted, nivolumab/ipilimumab or nivolumab alone may be continued as outlined in the protocol treatment schema if not meeting discontinuation rules and adverse event(s) has recovered to grade 1 or baseline and patient has successfully tapered of corticosteroids (and other immune modulatory agents). An exception is grade 2 endocrine disorders that can be treated with hormone replacement. When it is unclear how to manage the adverse event, hold drugs and consult the principal investigator.

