
Grade 2 AST or ALT > 3.0 x ULN to ≤ 5 x ULN or total bili > 1.5 x ULN to ≤ 3 x ULN
	
 • Cabozantinib: 
 – Interrupt cabozantinib dosing. – If LFTs return to baseline grade, resume cabozantinib at a reduced dose. • Nivolumab/Ipilimumab or Nivolumab: 
 – Hold therapy per protocol. – If LFTs return to baseline grade, resume therapy per protocol 	
 • Monitor LFTs twice weekly or more frequently as deemed clinically necessary. • If tapering off steroid therapy, monitor LFTs once weekly or more often per clinical judgment • If LFTs return to baseline grade, resume with routine monitoring • If LFT elevations persist > 7 days or worsen: 
 – Administer 0.5-1 mg/kg/day methylprednisolone or oral equivalent – When LFTs return to baseline grade or CTCAE Grade ≤1, taper steroids over at least 4 weeks – Add prophylactic antibiotics for opportunistic infections if on immune suppression > 1 month or prior to 1 month per investigator decision.

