9.2 Prohibited or Restricted Therapy

The following therapies are prohibited until study treatment has been permanently discontinued:

- Any investigational agent or investigational medical device.
- Oral anticoagulants with coumarin agents (eg, warfarin), direct thrombin inhibitor (e.g., dabigatran), direct factor Xa inhibitor betrixaban, antiplatelet agents such as clopidogrel, or chronic use of aspirin above low dose levels for cardioprotection (per local applicable guidelines) until 4 weeks after cabozantinib has been permanently discontinued.
- Any nonprotocol systemic anticancer treatment (eg, chemotherapy, immunotherapy, radionuclides, drugs or herbal products used specifically for the treatment of the cancer under investigation).
- Systemic corticosteroids above adrenal gland cortisol replacement levels (e.g. > prednisone 7.5 daily or equivalent) at study entry are not permitted. Use of corticosteroids above this level while on study may be required for management of immune related adverse events. Nivolumab and ipilimumab are held/discontinued while patients are on high dose corticosteroids and subsequent taper. Once steroid taper completed, patients may restart nivolumab and/or ipilimumab based on management guidelines in section 8.4. Patients may restart cabozantinib during steroid taper if adverse event is improved to grade 1 or better and management guidelines in section 8.3 are followed.

The following therapies should be avoided until study treatment has been permanently discontinued or until otherwise specified:

- Local anticancer treatment including palliative radiation, ablation, embolization, or surgery with impact on tumor lesions should not be performed until radiographic progression per imRECIST 1.1 has been established.
- Erythropoietic stimulating agents (eg, epoetin alfa and darbepoetin alfa) should not be used based on a report of increased risk of tumor recurrence/progression associated with erythropoietin (Wright et al 2007).
- Concomitant medications that are known to prolong the QTc interval should be avoided in subjects who receive cabozantinib until they have permanently discontinued cabozantinib treatment (refer to <http://www.qtdrugs.org> for a list of drugs which have the potential to prolong the QTc interval).

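### Steroid dose floor (1 versus 0.5 mg/kg/day) and the steroid level allowed when restarting ipilimumab are stated differently for the same immune event during induction

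*Combined protocol and SAP*

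**What the plan says.** **Starting dose.** Sections 8.3.6 (nivolumab) and 8.4.6 Adverse Events (ipilimumab) contain almost the same sentence for immune-related events of Grade 2 and above. The nivolumab version foresees "administration of high dose corticosteroids (1-2mg/kg/day of prednisone or equivalent) tapered off over a 4-6 week period". The ipilimumab version foresees "administration of high dose corticosteroids (0.5-2mg/kg/day of prednisone or equivalent) tapered off over a 4-6 week period". In Section 8.5, the Grade 2 row of Table 8-10 (liver toxicity) reads "Administer 0.5-1 mg/kg/day methylprednisolone or oral equivalent", subject to the condition "If LFT elevations persist > 7 days or worsen". The Section 8.5 text adds that for Grade 2 transaminase elevation "it may be appropriate to hold all study drugs, but monitor for improvement prior initiation of corticosteroids".

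**Steroid level at restart.** The text of 8.4.6 says "Patient are to be completely off prednisone unless used for adrenal replacement purposes prior to resuming any immunotherapy", and 8.3.6 carries the same sentence. Each adds an exception for cases discussed, with the Principal Investigator in 8.3.6 and with the Study Chair in 8.4.6. Section 9.2 agrees with the text: "Once steroid taper completed, patients may restart nivolumab and/or ipilimumab based on management guidelines in section 8.4". Section 8.5 also requires steroids to have been tapered off, in the setting where cabozantinib cannot be restarted. Table 8-9, to which 8.4.6 sends the reader, instead resumes ipilimumab after a Grade 2 reaction that has resolved to Grade 0-1 in patients "who are receiving less than 7.5 mg prednisone or equivalent per day". Footnote a of Table 8-8 (nivolumab) asks only for improvement to Grade 0 or 1 and does not mention steroids.

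**The concern.** Nivolumab and ipilimumab are given on the same days in induction, so one immune event falls under both drug sections at once. If the two sections set different floors, a site following one can be outside the other. If the text and the table of the same ipilimumab section set different restart conditions, whether a given subject may restart depends on which is consulted. No passage says which prevails when both drugs are being given.

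Steroid exposure and the timing of restart are at stake. The documents should direct both uniformly in a small single-arm trial (23 subjects for the primary analysis, up to 27 enrolled) that reports adverse event rates and discontinuation for adverse events as secondary endpoints.

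**Working it through.** The plan states no summary figure to reproduce. The check sets the rules side by side.

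**1. Do both sections apply?** Section 5.2 gives nivolumab and ipilimumab together every 3 weeks for 4 cycles. A Grade 2 or higher immune event in that period is therefore under 8.3.6 and 8.4.6 together.

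**2. Dose ranges (mg/kg/day).**

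| Source | Scope | Range |
|---|---|---|
| 8.3.6 | Grade 2 and above | 1 to 2 |
| 8.4.6 Adverse Events | Grade 2 and above | 0.5 to 2 |
| Table 8-10, Grade 2 row | liver only; persisting > 7 days or worsening | 0.5 to 1 (methylprednisolone or oral equivalent) |

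- 8.3.6 against 8.4.6: the overlap is 1 to 2. Doses from 0.5 to just under 1 fit only 8.4.6.
- 8.4.6 against Table 8-10: 0.5 to 1 lies wholly inside 0.5 to 2, so there is no conflict.
- 8.3.6 against Table 8-10: taking the two steroids as equal, the overlap is the single value 1. Below 1 breaches the 8.3.6 floor; above 1 exceeds the Table 8-10 ceiling.

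Ratio of floors: 1 / 0.5 = 2, whatever the body weight. For an assumed 80 kg subject, 80 × 0.5 = 40, 80 × 1 = 80 and 80 × 2 = 160, so the ranges are 80-160, 40-160 and 40-80 mg/day in table order.

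**3. Does steroid equivalence remove the third mismatch?** The documents give no conversion factor. Assuming 1 mg methylprednisolone equals 1.0 to 1.25 mg prednisone, the Table 8-10 range runs from 0.5-1 (factor 1.0) to 0.5 × 1.25 = 0.625 and 1 × 1.25 = 1.25 (factor 1.25). The lower end stays below 1. A factor of 1 / 0.5 = 2 would be needed to lift it to the 8.3.6 floor.

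**4. Restart of ipilimumab after a Grade 2 event, now Grade 0-1.** The cases assume prednisone for a non-replacement reason and no discussion with the Principal Investigator or Study Chair.

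| Prednisone at the visit | Text of 8.3.6 and 8.4.6 | Section 9.2 | Table 8-9 |
|---|---|---|---|
| none, taper finished | may restart | may restart | may restart |
| e.g. 5 mg/day, still tapering | may not | may not | may restart (5 < 7.5) |
| 7.5 mg/day or more | may not | may not | may not |

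The rules disagree only in the band above 0 and below 7.5 mg/day. Section 9.2 cannot settle it: it refers to Section 8.4, which holds both the text and the table.

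**5. Time at stake.** The stated taper is 4-6 weeks and the induction interval is 3 weeks: 4 / 3 = 1.3 and 6 / 3 = 2 cycles. That is the length of the whole taper, not the difference between the rules. The difference is only the final stretch from 7.5 mg/day to zero. The documents give no taper steps, so it cannot be computed, but it is shorter than the full taper.

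**6. Are doses lost?** Sections 8.3.6, 8.4.6 and 8.5 each allow later visits, scans included, to be moved after a delay so that all 4 induction cycles are completed, when the subject is eligible to restart both drugs. The direct effect is therefore on when dosing resumes.

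**The case against.** The strongest reply has four parts.

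- **The dose ranges are broad by intent.** Both sentences cover Grade 2 and above and are hedged on whether steroids are needed. Table 8-10 breaks the dose down by grade (0.5-1, then 1.0-2.0, then 2.0), which together spans 0.5-2 and agrees with 8.4.6. This stands, and it isolates the 1 mg/kg floor in 8.3.6 as the figure that does not fit. It does not reconcile that floor with the other two places.
- **Section 8.5 already routes overlapping events.** Both drug sections refer to it, 8.2.4.1.11 sends liver toxicity there, and it says to hold drugs and consult the principal investigator when management is unclear. This lowers the chance of divergent practice, especially for liver events. But 8.5 itself refers back to the standard nivolumab or ipilimumab guidelines, and nowhere ranks them.
- **The restart rule has exceptions.** Adrenal replacement is exempt, and Section 9.2 uses prednisone 7.5 mg as its example of that level, so much of the Table 8-9 band may be replacement use. Cases may also be discussed. This narrows the conflict to low-dose, non-replacement prednisone in an undiscussed case. Table 8-9 restricts itself to neither exception, so the conflict remains.
- **A subject off prednisone satisfies every rule.** True, but the documents do not say that the stricter text overrides the table.

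A reader might go further and infer that every Grade 2 immune event meets three conflicting ranges. The documents do not support this: Table 8-10 is for liver toxicity only and applies only after its trigger, so other events meet two ranges. Nor does footnote a of Table 8-8 contradict the text. It is silent on steroids, and 8.3.6 and 9.2 supply the condition.

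**Conclusion.** Two internal contradictions hold. First, the steroid floor during combined dosing is 1 mg/kg/day in 8.3.6 and 0.5 mg/kg/day in 8.4.6, a two-fold difference for the same event. Table 8-10 falls on the 0.5 side for Grade 2 liver toxicity that persists or worsens. Second, a subject at Grade 0-1 still tapering below 7.5 mg/day for a non-replacement reason may restart ipilimumab under Table 8-9. The text of 8.3.6, 8.4.6 and 9.2 does not allow it, unless the case is discussed as 8.3.6 and 8.4.6 permit.

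The consequence is that steroid exposure and time of restart depend on the passage read. It may be tempting to conclude that 1 to 2 of the 4 induction doses are lost. That does not follow: the figure measures the entire taper, and visits may be shifted to complete all 4 cycles. Nor do the documents show a bias in the endpoints. Steroid exposure is not an endpoint, a hold is not a discontinuation, and there is no comparator arm. The Simon two-stage figures are unaffected.

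The dose and restart contradictions rest on the text alone. The 80 kg weight and the 1.0-1.25 conversion factor are assumptions used for illustration, and neither conclusion depends on them within the range shown.

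**What to change.** The sponsor's clinicians should reconcile 8.3.6, 8.4.6 Adverse Events, Table 8-9, the Grade 2 row of Table 8-10 and Section 9.2, so that the steroid ranges agree and one steroid condition governs resumption of immunotherapy. Table 8-8 footnote a and the Section 8.5 text should be aligned with the result, and the protocol should state which passage prevails when nivolumab and ipilimumab are given together. No dose or restart rule is proposed here; that choice is clinical.

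The cost is a wording amendment with the review and approval that Section 15 requires. Sample size, decision boundaries and the analysis do not change.

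### Section 8.3.6 permits maintenance nivolumab after an ipilimumab-attributed induction irAE with no upper grade, while Table 8-8 ends nivolumab after grade 4 colitis

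*Combined protocol and SAP*

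**What the plan says.** Section 8.3.6 deals with immune-related adverse events of grade 2 and above. For those who have recovered from such an event that arose in induction on the combination, it states: "patients will be permitted to receive maintenance nivolumab if the irAE was most likely due to ipilimumab (e.g. immune colitis or hepatitis". Clinical benefit is a further requirement of that sentence. A separate condition in the same paragraph is that patients be "completely off prednisone unless used for adrenal replacement purposes prior to resuming any immunotherapy, unless discussed with the Principal Investigator". The preceding sentence refers to Table 8-8 and published guidelines, and the section opens with "Also refer to section 8.5 for management guidance on potential overlapping adverse events from nivolumab, ipilimumab and cabozantinib".

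Table 8-8 gives the nivolumab actions:

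- "Grade 4 diarrhea or colitis": permanently discontinue.
- Grade 3 diarrhea or colitis: withhold when nivolumab is a single agent, but "Permanently discontinue when administered with ipilimumab".
- Hepatitis without hepatocellular carcinoma, "AST or ALT more than 5 times the ULN or total bilirubin more than 3 times the ULN": permanently discontinue.
- "Life-threatening or Grade 4 adverse reaction": permanently discontinue.
- Events marked withhold: footnote a lets nivolumab resume at grade 0 or 1.

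Section 8.5 covers overlapping toxicity. Its Table 8-10 lets nivolumab resume after a grade 3 liver event on the combination, once liver tests are back to baseline grade and with Principal Investigator approval. It has no such exception for grade 4. For colitis there is no corresponding table. Section 8.5 says that ipilimumab-attributed grade 3 diarrhea calls for stopping drug, without saying which drug or whether nivolumab may later be given alone.

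**The concern.** The permission and the table give opposite instructions for the same patient, and nothing says which governs. Take a patient with grade 4 immune colitis in induction that is judged due to ipilimumab and resolves, with the tumor responding. The 8.3.6 sentence names colitis as an example and says such patients will be permitted maintenance nivolumab. Table 8-8 says nivolumab is over for that patient.

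What is at stake is patient safety: re-exposure to an anti-PD-1 antibody after a life-threatening immune event. It is a contradiction between two stated rules, not a missing detail.

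**Working it through.** No arithmetic decides this point. The check is to compare the rules event by event.

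| Event in induction, attributed to ipilimumab, recovered, patient benefiting | Section 8.3.6 sentence | Table 8-8 (nivolumab) | Section 8.5 / Table 8-10 | Result |
|---|---|---|---|---|
| Grade 2 colitis | Permits | Withhold; resume at grade 0-1 (footnote a) | No colitis table | Agree |
| Grade 3 colitis | Permits | Permanently discontinue when given with ipilimumab | Stop drug; drug not named | Depends on reading |
| Grade 4 colitis | Permits | Permanently discontinue (own row and general grade 4 row) | No colitis table | Conflict |
| Grade 3 hepatitis | Permits | Permanently discontinue | May resume with Principal Investigator approval | Largely settled by Table 8-10 |
| Grade 4 hepatitis | Permits | Permanently discontinue | Discontinue; exception is for grade 3 only | Two specific tables agree against one general sentence |

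**Grade 3 colitis.** The cell separates nivolumab as a single agent from nivolumab with ipilimumab. It can mean that nivolumab itself ends, which contradicts 8.3.6. It can also mean that the combination ends and nivolumab alone may follow, which does not.

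**Other events.** Colitis and hepatitis are only examples in 8.3.6. Literally, the sentence also reaches ipilimumab-attributed grade 3 pneumonitis, adrenal insufficiency or myocarditis, each a permanent stop in Table 8-8. A plain grade 3 cap would therefore not cure the wording.

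**Is there an approval step?** Three nearby texts were checked.

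1. In 8.3.6, "please consult study chair for approval to restart prior to the next scheduled treatment visit" applies to an early restart within induction after all drugs were held. It does not cover entry to maintenance.
2. The Principal Investigator discussion in 8.3.6 concerns resuming immunotherapy while still on prednisone. A patient who has finished the taper does not need it.
3. The end of the first paragraph of Section 8.5 tells sites to hold drugs and consult the principal investigator when management is unclear. This would catch the conflict if the site sees one.

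**How often.** The only colitis rate from a large trial in the protocol is Table 3-1 (CheckMate 067, nivolumab 1 mg/kg plus ipilimumab 3 mg/kg): grade 3-4 colitis in 26 of 313, or 8.3%. Applied to 27 enrolled subjects, 27 × 26/313 = 2.2. The share arising in induction is not given. Assuming 25% to 100%, the range is 0.25 × 2.2 = 0.6 to 2.2 subjects with grade 3-4 colitis.

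This is background only. It pools grades 3 and 4, and it comes from a different dose ratio. Section 3.3 reports fewer grade 3-4 treatment-related events overall with the ratio used here (34% versus 48%). The grade 4 part cannot be separated. In the phase 1 study of the triplet (Section 3.5, 18 subjects), the one grade 3-4 colitis case apparently arose in maintenance, since the colitis discontinuation is placed there.

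**The case against.** The strongest reply is that the protocol already contains the answer. The permission comes straight after a reference to Table 8-8, so it can be read as operating within that table. On that reading it still has work to do. Under Table 8-9, a grade 2 event lasting six weeks or longer ends ipilimumab, while Table 8-8 footnote a may still let nivolumab resume. The grade 3 colitis cell can be read as ending only the combination. Section 8.5 makes continued immunotherapy conditional on not meeting discontinuation rules, and Section 9.2 ties restart after a steroid taper to the management guidelines. Section 8.5 also supplies the default of holding drugs and consulting the principal investigator.

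Much of this stands. It shows that the authors probably did not intend nivolumab after grade 4 colitis. It does not remove the defect:

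- The 8.5 condition is written for patients who cannot restart cabozantinib.
- Section 9.2 points to Section 8.4, the ipilimumab section, whose Table 8-9 gives no nivolumab rule.
- The consult-if-unclear default depends on the site having a doubt, and a sentence saying patients will be permitted nivolumab does not raise one.

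A reader might also infer stronger points that the documents do not support:

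- *That 8.3.6 is a deliberate override of Table 8-8 reaching grade 4.* No text says so.
- *That grade 4 hepatitis is equally open.* Both tables bar nivolumab there, and 8.3.6 and 8.2.4.1.11 both point to Section 8.5.
- *That sites have no route to advice, or will in fact diverge.* Section 8.5 gives a route, and divergence is only possible.
- *That the pooled colitis rate measures the number of affected patients.* It does not isolate grade 4 or induction.

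**Conclusion.** The point holds in a narrow form. As written, Section 8.3.6 permits maintenance nivolumab after recovered grade 4 colitis attributed to ipilimumab, and Table 8-8 forbids it. Grade 3 colitis on the combination is ambiguous because of one cell. Hepatitis is largely settled.

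The number of patients affected cannot be derived from the documents and is likely small among 27; it may be none. The conclusion rests on a literal reading of the 8.3.6 sentence and on the absence of any statement of precedence.

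The primary test is unaffected: the two-stage cut-offs of 7 of 14 and 16 of 23 do not involve this rule. A reader might expect the discontinuation endpoint to shift, but an any-drug rate should hardly move, because Table 8-9 already ends ipilimumab permanently for grade 3-4 colitis and hepatitis. The case for acting is that the rule concerns life-threatening toxicity and can be corrected in a sentence.

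**What to change.** Add to the 8.3.6 sentence: *subject to Tables 8-8 and 8-10: not after any grade 4 event or any other event for which Table 8-8 requires permanent discontinuation, except grade 3 hepatitis on the combination as allowed in Table 8-10 with Principal Investigator approval.*

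In the grade 3 colitis cell of Table 8-8, state whether nivolumab alone may resume after recovery to grade 0-1. If it may, require Principal Investigator approval, as for grade 3 hepatitis. Which answer is right for grade 3 colitis is a clinical decision for the investigators.

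Leave grade 2 restarts under footnote a as they are; they need no new approval.

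The cost is a text amendment to one sentence and one table cell, with no extra patients or assessments. The only downside is one approval step for rare grade 3 colitis restarts, if those are allowed.
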